10.2.1 Analysis of the Primary Endpoint

The primary endpoint in this study is objective response rate per cohort, defined as the percentage of patients in each cohort with a CR or PR, measured at the first scheduled disease assessment following study treatment initiation (Day 84, \pm 7 days) as assessed by the IRC according to RECIST v1.1, or

RECIST v1.1 combined with biomarker assessment, or IPCG response criteria or the 'Lugano' response using the FDG-PET-CT 5-PS and assessment of EBV load.

Results will be expressed as a percentage of the analysis population with a 95% exact confidence interval.

Patients who withdraw from the study prior to this time point or who have non-evaluable disease will be considered as 'non-responders' in this analysis.

10.3 Statistical Rules for Trial / Early Trial Termination

The trial as a whole or individual cohorts may be stopped early based on the outcome of scheduled interim analyses (see Section 10.2). Individual cohorts may also be closed if a minimal level of accrual (10 patients in the 2 years after activation of the first site) is not achieved.

Note: Patients who are discovered to have been incorrectly assigned to a cohort (e.g. following reevaluation of a diagnostic sample) prior to evaluation of their response will be considered as "nonevaluable" in this interim analysis.

Continuation of treatment of incorrectly assigned patients must be discussed and approved by the coordinating Investigator according to the individual benefit-risk ratio.

The same futility rule is applied to all the k cohorts at each interim analysis.

Early stopping for futility is based on the current posterior probability that p is lower than p0

$$P(p_k < p_{0k} | y_{ki}, n_{ki}) > \gamma_k$$
 (equation 1)

where p_{0k} defines the minimal probability of efficacy under which the treatment appears ineffective; it will be fixed at a minimum level of 0.10 in each cohort; the decision threshold γ_k may also depend on the cohort (Berry 2013). It usually lies in (0.8,0.9).

Note: This early stopping for futility rule is applicable for all cohorts except the rare ovarian cancer cohort (see Section 10.2).

Additionally, we will use a stopping criterion for efficacy if the probability that the response rate, p_k , is greater than p_{1k} , is higher than 90%:

$$P(p_k > p_{1k}|y_{ki}, n_{ki}) > 0.9$$
 (equation 2)

where p_{1k} defines the minimal probability of efficacy over which the treatment appears effective; it will be fixed at a minimum level of 0.50 in each cohort.

Note: if available scientific data warrant, the Steering Committee may modify the minimal probability levels of a given cohort before the first interim analysis.

The prior parameters will be chosen to insure non informative either Jeffreys' or uniform prior distributions.

The second stage will be based on the comparison of response rates across subsets based on predictive biomarkers in the selected cohorts. It will be based on the comparison of response rates across subsets (any a and b in 1,,..., k) as follows

$$P(p_a - p_b > 0 | y_i, n_i) > 85\%$$
 (2) (equation 3)

Such subset analyses will result in potentially sub-cohorts of poor outcomes that may be proposed for discontinuation while those of good outcomes will enrich the design (Mandrekar 2009; Zang 2016).

In the absence of a decision to halt enrolment, accrual in each cohort will continue until the end of the planned of recruitment period (3 years after activation of the first site) or a maximal accrual of 50 patients is achieved (whatever occurs first) unless promising results have allowed some cohorts to include more patients.

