The first stage treats all patients from the different cohorts with the investigational product and identifies possibly sensitive subpopulations (Berry 2013). The second stage will compare response rates across subsets within the selected cohorts (Trippa 2012).

The first stage will analyse data in each cohort independently of each other. Interim analysis of the ORR according to investigators' assessment is planned after 10 first patients eligible enrolled in the cohort have completed the first scheduled disease evaluation. Based on the estimated response rate and its posterior distribution in each cohort, cohorts that do not reach a minimal ORR of 0.1 (85% confidence) will be potentially closed to further recruitment. In addition, individual cohorts may also be closed during stage 1 if a minimal level of accrual (10 patients in the 2 years after activation of the first site) is not achieved.

In the second stage, intra-cohort analyses will be performed after every 5 additional patients accrued (Berry 2013). These analyses will use all data accumulated up to that point, and will consider potential predictive markers of efficacy; such subset analyses will result in potentially sub-cohorts of poor outcomes that may be proposed for enrolment discontinuation while those of good outcomes will enrich the design (Mandrekar 2009; Zang 2016). In the absence of a decision to halt enrolment, accrual in each cohort will continue until the end of the planned recruitment period (3 years after activation of the first site) or a maximal size by cohort of 50 patients (whatever occurs first) except for the cohorts that were amended where the maximal number of patients may be increased.

Final analysis of efficacy endpoints will be performed using both the Investigator and IRC assessment of response according to: (i) RECIST v1.1, (ii) RECIST v1.1 combined with biomarker assessment (iii) IPCG response criteria, or (iv) Lugano 5-PS criteria. Comparisons between Investigator and IRC results will also be reported. Point estimates will be provided with 95% confidence intervals. Predictive analyses of response will be performed.

All analyses will be performed for the primary cohort and the Re-challenge cohort, separately.

F) SAMPLES COLLECTED FOR TRANSLATIONAL RESEARCH

SAMPLE TYPES:

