In the absence of a decision to halt enrolment, accrual in each cohort will continue until the end of the planned of recruitment period (3 years after activation of the first site) or a maximal accrual of 50 patients is achieved (whatever occurs first). In case of promising subtypes, enrolment could increase possibly above the pre-established limit of 50 patients, unless the maximal sample size of 350 patients has been reached or the termination date of study enrolment. There is no drawback from a statistical point of view that sample size of cohorts will differ from one another, while increased subsamples may allow more accurate estimates of the outcome in those subsets.

Note: Patient enrolment will be suspended for each cohort following the inclusion of the 10 first patients eligible until the outcome of the interim analysis is known. Enrolment may be reopened prior to the interim analysis upon the decision of the Steering Committee if there is a recognised clinical need and provided that at least one response has been observed and confirmed by a collegiate revue.

Rare ovarian cancer cohort: due to the aggressively of this disease and the prognostic heterogeneity between ovarian cancer subtypes with the difficulties this poses in the interpretation of response rate, the decision to continue enrolment in this cohort will also take into account the number of patients with stabilisation of their disease. Recruitment to this cohort will continue (up to 50 patients) if $\geq 4/10$ patients achieve at least stable disease at their first disease evaluation. Response rate will be subsequently reevaluated for each histological subset following the inclusion of the 10 first patients of each type with the application of the stopping rule as outlined below. In the subset of promising subtypes (teratoma and low-grade serous carcinoma), enrolment will increase possibly above the pre-established limit of 50 patients.

Final analysis of efficacy endpoints will be performed using both the Investigator and IRC assessment of response according to RECIST v1.1, or RECIST v1.1 combined with biomarker assessment, or IPCG response criteria, or the 'Lugano' response using the FDG-PET-CT 5-PS and assessment of EBV load. Comparisons between Investigator and IRC results will also be reported.

Statistical data will be expressed in the form of:

- Frequencies and Percentages (qualitative variables),
- Mean and standard deviation

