11.3 Steering Committee

A Steering Committee has been implemented for this trial. The Steering Committee will meet on a quarterly basis. Additional meetings may be set, as required.

The Steering Committee is composed of:

- The Coordinating Investigator
- The Biostatistician
- Project Manager (or delegate)
- Representative(s) of INCa
- Pathology expert(s) designated for each pathology cohort
- Other participants as required depending the meeting agenda.

Representative(s) of the IP license holder (Merck Sharp & Dohme) will also be invited to attend at least once per semester.

The Steering Committee will review the accumulated data regarding overall safety and efficacy of the study treatment, including the results of interim analyses, collated safety reports prepared by the Sponsor, as well as published data and information provided by the IP license holder concerning concurrent studies. The Steering Committee will also review, or may request, recommendations made by the IDMC. The Steering Committee, based on this information, will assist the Sponsor in resolving issues and/or questions encountered during the conduct of the trial and will make recommendations regarding continued recruitment or termination of enrolment in each cohort, or if new cohorts/indications should be considered.

Any recommendations which would result in substantial modifications to the conduct of the study, amendment of the protocol design, or the introduction of new indications must obtain approval from the ANSM and EC prior to implementation (see Section 14.5).

The roles and responsibilities of the Steering Committee are further detailed in the Steering Committee Charter.

The Coordinating Investigator will generate minutes of each meeting and report the outcome of Steering Committee meetings to the IAPC (see Section 11.4).

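### A cohort's p0 and p1 may be changed until the first interim analysis, a cutoff that does not precede the responses the Steering Committee can already see

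*Protocol*

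**What the plan says.** Protocol section 10.3 stops a cohort for futility when the posterior probability that its response rate is below p0 exceeds a threshold γ (equation 1). Of p0 it says "it will be fixed at a minimum level of 0.10 in each cohort". It stops for efficacy when the posterior probability that the rate exceeds p1 is above 0.9 (equation 2). Of p1 it says "it will be fixed at a minimum level of 0.50 in each cohort". A note then adds: "if available scientific data warrant, the Steering Committee may modify the minimal probability levels of a given cohort before the first interim analysis".

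The synopsis gives the futility confidence: "cohorts that do not reach a minimal ORR of 0.1 (85% confidence) will be potentially closed to further recruitment". Section 10.3 gives only a usual range of 0.8 to 0.9 for γ and leaves the prior open: "The prior parameters will be chosen to insure non informative either Jeffreys' or uniform prior distributions".

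On who sees what before the interim, section 11.3 states: "The Steering Committee will review the accumulated data regarding overall safety and efficacy of the study treatment". Interim results are named there as one part of those data. The committee includes the coordinating investigator, the biostatistician and each cohort's pathology expert, and meets quarterly. Section 10.2 suspends enrolment after the first 10 eligible patients but lets the same committee reopen it ahead of the interim, "provided that at least one response has been observed and confirmed by a collegiate revue".

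**The concern.** A rule that lets a threshold move before the interim protects the decision only if those who move it do not yet know the outcomes it will judge. Here the deadline is the formal look, not the arrival of data. Treatment is open-label, the interim uses the investigators' own response assessments, and the committee that may change p0 and p1 is expected to know about responses in the cohort. The note does not restrict the scientific data to sources outside the trial.

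What is at stake is the first-look classification of a cohort: closed for futility, continued, or stopped for efficacy. If the reference value can be chosen with the responses in view, the classification appears to follow a rule while it may partly reflect the data being judged.

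**Working it through.** **Inputs.** p0 = 0.10, p1 = 0.50, efficacy probability 0.9 (section 10.3); futility confidence 0.85 (synopsis, statistical analysis); first look at n = 10 with Day-84 assessment done (section 10.2); Jeffreys or uniform prior (section 10.3); accrual of 10–15 patients per cohort per year (section 10.1); quarterly meetings (section 11.3). The protocol states no error rate or power for these rules, so there is no planned figure to reproduce. All alternative thresholds below are illustrative assumptions.

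**Timing.** Ten patients take 10/15 year = 8 months to 10/10 year = 12 months to enrol. Adding 84 days (about 2.8 months) gives about 11 to 15 months to the last assessment. No Day-84 result exists in the first 84 days, so results are accumulating for about 8 to 12 months. At one meeting every 3 months that is roughly 2 to 4 meetings, the earliest with very few patients assessed.

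**Formula.** With y responses in 10, the posterior is Beta(a + y, b + 10 − y), with a = b = 1 (uniform) or a = b = 0.5 (Jeffreys). For 0/10 and the uniform prior this is Beta(1, 11), so P(p < p0) = 1 − (1 − p0)^11:

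- p0 = 0.10: 1 − 0.9^11 = 1 − 0.314 = 0.686, below 0.85, continue.
- p0 = 0.20: 1 − 0.8^11 = 1 − 0.086 = 0.914, above 0.85, stop.

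**With the stated thresholds held fixed.** Futility: Jeffreys stops only at 0/10 (0.858); uniform never stops at n = 10. Efficacy: both priors stop at 8/10 or more (0.967 uniform, 0.974 Jeffreys) and not at 7/10 (0.887, 0.898).

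**With a changed threshold.**

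| Data | Prior | Quantity | At stated value | At assumed value | Direction |
|---|---|---|---|---|---|
| 0/10 | uniform | P(p < p0) | 0.686 at 0.10, continue | 0.914 at 0.20, stop | up |
| 1/10 | Jeffreys | P(p < p0) | 0.439 at 0.10, continue | 0.867 at 0.25, stop | up |
| 8/10 | uniform | P(p > p1) | 0.967 at 0.50, stop | 0.881 at 0.60, no stop | up |
| 0/10 | Jeffreys | P(p < p0) | 0.858 at 0.10, stop | 0.809 at 0.08, continue | down |
| 5/10 | either | P(p > p1) | 0.50 at 0.50, no stop | 0.91–0.92 at 0.30, stop | down |

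The upward rows are possible on any reading of the note. The downward rows are possible only if the stated minimum levels are not floors.

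The p0 above which a cohort stops (γ = 0.85) is 0.158 uniform or 0.096 Jeffreys for 0/10, and 0.275 or 0.239 for 1/10. For 8/10 under Jeffreys, p1 = 0.60 still gives a stop (0.906).

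**How often such counts arise.** At a true rate of 0.10, P(0/10) = 0.9^10 = 0.349 and P(0 or 1 of 10) = 0.736, so low counts at the first look are not rare.

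**The case against.** **The minimum levels may be floors.** Section 10.3 fixes p0 and p1 at a minimum level just before the note. If those are floors, nobody can rescue a 0/10 cohort by lowering p0 or call 5/10 effective by lowering p1. A reader might infer both, and might add that at a true rate of 0.30 the chance of an efficacy stop at the first look goes from 0.2% (8/10 needed) to 15% (5/10 needed). That inference holds only if downward changes are allowed, and the protocol does not establish this. The upward changes remain either way, although closing a 1/10 cohort needs p0 above 0.239 or 0.275.

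**No issued decision can be overturned.** This is correct. The power ends before the first interim, so the outcome can only differ from what the stated thresholds would have produced.

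**Closure is discretionary anyway.** The synopsis and section 10.2 speak of potential closure, the IDMC is consultative, and the sponsor and Steering Committee decide. This limits the added harm. But overriding a stated rule is visible, whereas moving its reference value is less so.

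**The note probably means external evidence.** The protocol calls trial results accumulated data and lists published and licence-holder information separately, so this is a fair reading, but the note does not say it.

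**Safeguards exist.** Section 10.6 requires changes to the analysis plan to be described and justified, and section 11.3 requires ANSM and ethics approval for substantial modifications. Neither is tied to this note, which authorises the change in advance. Documentation or approval would also not stop a change from depending on responses already seen.

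**The open prior matters too.** At p0 = 0.10, 0/10 is a stop under Jeffreys (0.858) and a continue under uniform (0.686). That is a separate source of latitude and does not remove this one.

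**Conclusion.** The point stands in a limited form. The cutoff in section 10.3 does not precede outcome data, and the committee holding the power reviews those data and may act on a response before the interim. Plausible threshold changes are enough to alter the first-look outcome at 0/10, 1/10 or 8/10 even if only increases are allowed, and also at 0/10 (Jeffreys) and 5/10 if decreases are allowed. These results rest on n = 10, γ = 0.85, the two named priors and assumed alternative thresholds. The count of 2 to 4 meetings rests on the planned accrual.

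The consequence is confined to stage-1 cohort selection and early stopping. A reader might infer that the primary result is compromised, but section 10.2.1 reports an IRC-assessed response rate with an exact 95% interval, which uses neither p0 nor p1. The ovarian cohort is also outside equation 1 at its first look, where section 10.2 applies a stable-disease criterion. Nothing in the protocol shows that any threshold was in fact changed on trial data. The wording should be tightened because the protection is nearly free.

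**What to change.** Replace the note in section 10.3 with text to this effect: *The Steering Committee may modify p0k or p1k of a given cohort only on documented data external to this trial, and only before the first post-baseline disease assessment of any patient in that cohort. The change, its source and its date are recorded and sent to the IDMC. After that point both values are fixed.* State in the same place whether 0.10 and 0.50 are floors.

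For cohorts already past that point, report the p0 and p1 used at the first look, and whether, when and on what data they were changed.

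The cost is a short rewording and a short disclosure. The sponsor gives up only the freedom to change thresholds after responses have been seen; external evidence can still be used earlier.

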10.2 Planned Statistical Analysis

The trial will use a two-stage Bayesian enrichment design, allowing for a smaller more informative trial that is specifically tied to decision making within a drug development program. This process allows for incremental changes to each cohort based on current data, rather than restricting revisions in a trial design using fixed sample sizes.

The first stage treats all patients from the different cohorts with the IP and identifies possibly sensitive subpopulations (Berry 2013). The second stage will compare response rates across subsets within the selected cohorts (Trippa 2012).

Let p0, define the rate of response that is considered uninteresting, and p1 a targeted level of interest. Let k, be the number of initially defined cohorts of patients. Let Y=0,1 define the response of patient I in the cohort k, and nki the total sample size.

We will model the probability of response, $\theta = P(Y=1)$, and will use a subscript to indicate patient cohort: $\theta_1, \theta_2, ... \theta_k$. This allows us to reflect the treatment effects in each group relatively to the targeted values. All inference and stopping rules on futility or efficacy will be based on the probability scale which is clinically interpretable (Berry 2013; Jacob 2016, Zalavsky 2013).

The first stage will analyse data in each cohort independently of the other cohorts. Interim analysis of the primary endpoint (ORR according to Investigator response assessment) is planned after the 10 first patients eligible have been enrolled in the cohort and completed the first scheduled disease evaluation.

Based on the estimated response rate and its posterior distribution in each cohort, cohorts that do not reach a targeted level of confidence in terms of minimal efficacy will be potentially closed to further recruitment.

In the second stage intra-cohort analyses will be performed after every 5 additional patients accrued (Berry 2013). These analyses will use all data accumulated up to that point, and will consider potential predictive markers of efficacy; such subsets analyses will result in potentially sub-cohorts of poor outcomes that may be proposed for enrolment discontinuation while those of good outcomes will enrich the design (Mandrekar 2009; Zang 2016).

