- Median and interquartile range (quantitative variables),
- Survival curve estimates calculated with the Kaplan Meier method (survival data) (Kaplan, 1958).

Each primary and secondary evaluation criterion will be reported with a confidence interval of 95%.

Multivariate predictive analyses of each endpoint will be performed with regression models: logistic regression (for the main end point), and Cox (for PFS and OS) models.

Gail and Simon statistics will be used to test if the disease features and the mutational load measured in tumour samples of certain cohorts is correlated with pembrolizumab efficacy on the primary end point.

Data will be analysed with the SAS (SAS Inc, Cary, NC) and R (https://www.R-project.org/) software packages

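### The Gail and Simon test has no treatment contrast in this single-arm trial, and the stage-2 subset rule (equation 3) has a high false-flag rate that the protocol does not state

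*Protocol*

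**What the plan says.** Two statements in the protocol deal with differences in response between subsets.

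The first is in Section 10.2: "Gail and Simon statistics will be used to test if the disease features and the mutational load" in certain cohorts is correlated with pembrolizumab efficacy on the primary endpoint. The sentence names no comparator or reference rate. The synopsis (Methodology) says that all included patients receive pembrolizumab.

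The second is the stage-2 rule. Section 10.2 states "In the second stage intra-cohort analyses will be performed after every 5 additional patients accrued" and adds "These analyses will use all data accumulated up to that point". The first interim analysis "is planned after the 10 first patients eligible have been enrolled in the cohort", so the stage-2 looks fall at 15, 20, ..., 50 patients. Section 10.3 states "The second stage will be based on the comparison of response rates across subsets based on predictive biomarkers in the selected cohorts" and gives the comparison "across subsets (any a and b in 1,,..., k) as follows": "P(p_a - p_b > 0 | y_i, n_i) > 85"%, under a Jeffreys or a uniform prior. The consequence is that "Such subset analyses will result in potentially sub-cohorts of poor outcomes that may be proposed for discontinuation". The protocol attaches no false-flag rate, power, general minimum subset size, or allowance for repeated looks or several pairs to this rule.

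**The concern.** Both tools serve the secondary objective of identifying populations expected to benefit (Section 2.2). A test that needs a control arm gives no answer in a trial without one, and a null or uncomputable result could be misread as absence of association.

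The 85% rule has a different problem. A cut-off of 85% under a flat prior allows roughly a 15% one-sided error per comparison. The rule works in both directions and is repeated on accumulating data, so chance differences have many opportunities to cross it. In rare histologies or marker groups, a subset proposed for closure by chance may not be studied again soon. The committees that receive the proposal are not told how often such a proposal arises by chance.

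**Working it through.** **Gail and Simon.** Let D_i be the estimated treatment effect in subset i and s_i its standard error. The test forms Q+ = sum of (D_i/s_i)² over subsets with D_i > 0 and Q− = the same sum over subsets with D_i < 0. It rejects when min(Q+, Q−) is large. D_i is a treatment-minus-control difference. With one arm there are two ways to supply a D_i, and neither answers the stated question:
- D_i = the raw response rate. It cannot be negative, so Q− = 0, min(Q+, Q−) = 0, and the test never rejects.
- D_i = the response rate minus a fixed value, for instance the futility level 0.10. The test then asks whether some subsets lie above 10% and others below. Two subsets at 15% and 60% differ by 45 points, but both lie above 10%, so again Q− = 0. The protocol does not define this version.

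**Equation 3: inputs.** From the protocol: cut-off 0.85, any ordered pair, looks every 5 patients from 15, cumulative data, cohorts of 20 to 50 (Section 10.1), and prior Beta(c, c) with c = 1 (uniform) or 0.5 (Jeffreys). Assumed, because the protocol gives no values: two subsets, random membership, the same true response rate in both, set between 10% and 40%. The protocol states no operating characteristic for this rule, so there is no figure of its own to reproduce.

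**Formula.** p_a given the data follows Beta(c + y_a, c + n_a − y_a), and likewise for p_b. P(p_a > p_b) = ∫ f_a(x) F_b(x) dx. A flag is raised if this exceeds 0.85 in either direction.

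**How little data is needed.** At 15 patients, take 1/5 responders against 0/10 under the uniform prior. The posteriors are Beta(2, 5) and Beta(1, 11), so P(p_b > p_a) = B(2, 16)/B(2, 5) = (1/272)/(1/30) = 0.110 and P(p_a > p_b) = 0.890. One responder raises a flag (0.92 under Jeffreys). At 20 patients, 3/10 against 1/10 gives 0.867 under Jeffreys (flag) and 0.845 under uniform (no flag). The protocol allows either prior, and here the choice decides the outcome.

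**Simulation.** Chance that one of two equally responsive subsets is flagged at least once (4,000 cohorts per setting, 50/50 split, ranges over the true rates):

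| Accrual | Flagged at some look |
|---|---|
| 20 | 23–45% (both priors) |
| 30 | about 37–57% (both priors) |
| 50 | 51–63% (uniform), 65–69% (Jeffreys) |
| 80 | 63–76% (both priors) |

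A single look at 50 gives about 26–33%, in line with 2 × 15% = 30%. The repeated looks roughly double it. For cohorts of 50, a 30/70 split gives 49–70%, a 20/80 split 45–69%, and applying the futility rule first 44–69% (both priors). Four equal subsets give 93–98%.

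**A stricter rule, for scale.** Require at least 10 patients per subset and a cut-off of 97.5%, with accrual to 50:
- False flags with two equal subsets: about 6–13%. With four equal subsets: 15–22%.
- Detection of 35% v 5%: 83–88%, against 98% under the present rule. With a 20/80 split: 41–44%.
- Detection of 30% v 10%: about 50%, against about 87% under the present rule.
- With a 20/80 split, the smaller subset fails to reach 10 of 50 patients with probability P(Bin(50, 0.2) ≤ 9) = 0.44.

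**The case against.** A reader might infer that half or more of the cohorts would have a subset wrongly closed. The documents do not support that. A flag leads only to a proposal. The IDMC is consultative (Section 11.2), and Steering Committee recommendations that substantially modify the study need regulatory and ethics approval (Section 11.3). The 50 to 70% also depends on accrual to 50, while Section 10.1 allows cohorts as small as 20. The number and size of the subsets are my assumptions. Equation 3 can be computed and can reasonably be read as a permissive screen. These limits stand. It remains true that the protocol fixes the cut-off, the pairwise form and the look schedule, and gives no error rate for them.

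A reader might also infer that there is no protection for small subsets at all. Section 10.2 does require 10 patients of each histology in the ovarian cohort before re-evaluation. That uses a stopping rule on the response rate and not equation 3, so equation 3 still has no general minimum.

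It may be argued that Gail and Simon statistics could be built against a reference such as 0.10, so calling the test always zero goes too far. That is correct: zero follows only if raw rates are used. But the protocol defines no reference, and that version would test whether subsets fall on both sides of it, which is not a test of association.

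Two further readings should be resisted. One is that the planned logistic regression is unstable because of few responders: this presumes a separate fit per cohort at a low response rate, which Section 10.2 does not state. The other is that the secondary objective rests only on these two tools: per-cohort ORR with exact intervals, the ovarian histology review and the regression models also serve it.

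**Conclusion.** The point on Gail and Simon holds without any assumption about data. The named test needs a treatment contrast that a single-arm trial lacks, the protocol supplies no substitute, and so it cannot show whether disease features or mutational load relate to response.

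The point on equation 3 is secondary and conditional. With two equally responsive, roughly equal-sized subsets, one is flagged at least once in about 50 to 70% of cohorts accruing to 50, 23 to 45% at 20 and about 37 to 57% at 30. These are rates of false proposals. The fault is a high false-flag rate that nobody has stated, in a rule that otherwise can be applied. The primary analysis of ORR per cohort (Section 10.2.1) does not use either tool and is unaffected.

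**What to change.** Section 10.2: replace the Gail and Simon sentence with an exact test of heterogeneity of Day-84 ORR across feature levels within cohort, and for mutational load a cohort-stratified exact or penalised logistic model. Report the results as associations with response, because one arm cannot separate prognostic from predictive effects. If a heterogeneity test was what the authors meant, the text should say so. This costs one or two sentences and no patients.

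Section 10.3: state the simulated false-flag rate and power of equation 3 for plausible numbers and sizes of subsets, name the prior, and describe a flag as a screening signal for the committees. Section 10.2 uses k for the number of cohorts, so equation 3 should index subsets by another symbol. Choose a minimum subset size and a cut-off above 85% from those simulations. Ten patients per subset and 97.5% is one option. Its cost is real: 30% v 10% would be detected in about 50% of cohorts instead of about 87%, small subsets would often never qualify, and it still makes no allowance for several subsets. The choice belongs to the trial team once the figures are in front of them.
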